3.4.2.2 Overview of Efficacy

An overview of data are provided below and described in detail in the rucaparib IB.

Efficacy analysis was based on pooled efficacy data from 106 patients with BRCA mutant ovarian cancer, who received 2 or more prior chemotherapy regimens, and who initiated treatment with rucaparib at 600 mg BID in Part 2A of Study CO-338-010 and Parts 1 and 2 of Study CO-338-017. The enrollment cut-off date was 1 October 2015 (all 42 patients enrolled) and the visit data cut-off date was 30 November 2015 for Study CO-338-010 Part 2A. The enrollment cut-off was a 1 October 2015 and the visit data cut-off was 29 February 2016 for Part 1 (24 patients) and Part 2 (40 patients) of Study CO-338-017.

Efficacy data indicate that many patients with advanced ovarian cancer associated with a BRCA1/2 mutation and who had 2 or more prior therapies achieve RECIST and/or GCIG CA-125 responses. The confirmed ORR per RECIST by investigator review was 53.8% (57/106) and the confirmed response by RECIST or GCIG-CA-125 was 70.8% (75/106). The confirmed ORR per RECIST by independent review was 41.5% (44/106).

In addition, patients without a BRCA1/2 mutation in tumor tissue are also deriving benefit, with 43% achieving RECIST and/or GCIG CA-125 responses.

In the Phase 3, randomized, double-blind study of monotherapy oral rucaparib versus placebo as switch maintenance treatment in patients with platinum-sensitive, relapsed, high-grade ovarian cancer who achieved a response to platinum-based chemotherapy (ARIEL3), the primary efficacy endpoint was investigator-assessed PFS (invPFS) by RECIST v1.1. Three patient populations (tBRCA, HRD, and intent-to-treat [ITT]) were evaluated in a step-down analysis.

The primary endpoint was achieved as of 15 April 2017 with a highly statistically significant difference in invPFS between rucaparib treatment as compared to placebo for each of the 3 stratified primary efficacy analysis populations ($p < 0.0001$ for each population). The median invPFS in the tBRCA population was 16.6 months (95% CI, 13.4-22.9) for the rucaparib group and 5.4 months (95% CI, 3.4-6.7) for the placebo group. Additional data in HRD and ITT populations are available in the rucaparib IB.

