If a patient has radiologic progression, but continues to derive clinical benefit per the investigator, then continuation of treatment beyond progression may be requested by the investigator as per [Section 7.4.4](#). In such cases, the decision to continue will be made jointly between the investigator and the sponsor (or designee), and the patient must consent prior to continuing treatment with rucaparib. These patients will continue to undergo all protocol required assessments specified in [Table 5](#).

Patient safety will be monitored on a regular basis using procedures and assessments described in [Section 9](#) and [Section 13.4](#). Safety data will be periodically reviewed by the Data Monitoring Committee (DMC) as described in [Section 13.6](#). The DMC will comprise study investigators and sponsor representatives. The DMC will meet after the first 20 patients received rucaparib for at least 28 days or discontinued study treatment, and then at least semi-annually after sufficient data has been collected.

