7.4.4 Treatment with Rucaparib beyond Disease Progression

Patients will receive rucaparib until confirmed radiologic disease progression as assessed by investigator using modified RECIST Version 1.1 ([Appendix 2](#)) and/or PCWG3 (for bone lesions only) ([Appendix 2](#)) criteria, unequivocal clinical disease progression, unacceptable toxicity or inability to tolerate further treatment, loss to follow-up, or withdrawal of consent. However, if a patient receiving rucaparib has met criteria for confirmed radiologic disease progression by modified RECIST Version 1.1 and/or PCWG3 criteria, but the patient continues to derive clinical benefit per the investigator, then continuation of treatment will be permitted with additional consent. Clinical scenarios where continuation of study drug treatment after radiographic progression may be considered include 1) a patient for whom radiographic progression develops slowly while disease-related symptoms remain well controlled, 2) a patient who experiences progression in a site of disease that is unlikely to adversely affect prognosis (eg, enlargement of a solitary lymph node), or 3) a patient with general disease control but limited progression in sites of disease that can be managed with local therapies such as surgery or radiation. Patients continuing to receive rucaparib will continue to have all protocol-required assessments as described in [Section 9](#), with the exception of radiographic assessments which may be performed per local standard of care.

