- ^k = Disease assessment by CT/MRI and bone scans will be performed during screening, during the treatment phase, and Treatment Discontinuation, and if applicable, during follow up. Modified RECIST 1.1/PCWG3 criteria will be used. If a CR or PR is noted, confirmatory scans should be performed at least 4 weeks after the initial response was first documented.

- ^l = Radiologic assessments should continue for all patients until confirmation of radiographic progression per investigator assessment, including any patient who discontinued from study treatment for reason other than disease progression or death. Tumor assessments should be performed during the Treatment Discontinuation visit, 28-day Follow-up, or during Long-term Follow-up if the reason was other than radiologically confirmed disease progression and it has been ≥ 8 weeks (≥ 12 weeks if previous scan was after 24 weeks on study) since the last assessment. Tumor assessments should continue on schedule (ie, every 8 or 12 weeks) during Long-term Follow-up until radiographically confirmed disease progression.
- ^m = If archival primary or metastatic tumor tissue was not submitted during Pre-Screening, a specimen should be submitted during the Screening period or after enrollment for retrospective testing by the central laboratory. Archival tissue submitted during Screening for retrospective testing can be > 3 years old. Refer to the Pathology Charter for detailed sample handling instructions.
- ⁿ = The BPI-SF, analgesic drug score, FACT-P, and EQ-5D-5L instruments should be completed prior to other scheduled study procedures and dosing (if applicable). During long term follow up, if possible, PROs to be collected to coincide on days when tumor assessments are performed.
- ^o = All PSA measurements are performed by the local laboratory. Serial PSA measurements that show progression at study entry must follow the protocol specification.

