9.5.5 Study Day 57 (Week 9) and Every 28 Days Thereafter

Patients will be instructed to refrain from taking their first dose of rucaparib at home on study visits when plasma samples are collected for PK.

Plasma samples for PK analysis should be collected before the morning dose on Study Day 57, Day 85, and Day 113 as close to 12 hours after the previous dose as possible. If the start of the next dose is delayed, the PK sample should still be collected during this visit instead of the delayed start of the next study visit;

The following procedures will be completed:

- PRO collected using the BPI-SF ([Appendix 6](#)), FACT-P ([Appendix 7](#)), EQ-5D-5L ([Appendix 8](#)), and analgesic drug score instruments ([Appendix 9](#); should be completed before other procedures)
- Physical examination
- Weight
- Vital signs
- Tumor assessment scans at the end of every 8 calendar weeks (± 7 days) for the first 24 weeks (Weeks 9, 17, 25), and then every 12 calendar weeks (± 7 days) thereafter (Weeks 37, 49, 61, etc)
- Concomitant medications and procedures
- ECOG performance status ([Appendix 3](#))
- PSA measurement
- Hematology

- Serum chemistry (fasting is not required)
- Urinalysis
- Plasma sample for ctDNA
- Plasma sample for PK analyses (Study Day 57, Day 85, and Day 113 only)
- AE (inclusive of SAE and AESI) monitoring
- Dispensation of rucaparib

Patients will ingest rucaparib twice daily at about the same times every day as close to 12 hours apart as possible. Rucaparib should be taken with at least 8 oz (240 mL) of water with or without food. Patients will keep all unused containers (empty, partially used, and/or unopened) and return with them to the study site for accountability at the next visit. In the event of toxicities, re-treatment or dose modification will be according to the criteria described in [Section 7.4.2](#).

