9.6 Post-treatment Phase

9.6.1 Treatment Discontinuation Visit

Upon treatment discontinuation, regardless of the reason, patients will have a Treatment Discontinuation Visit. However, patients receiving rucaparib with radiologic disease progression by modified RECIST Version 1.1 and/or PCWG3 criteria (for bone lesions), as assessed by the investigator, but still receiving benefit, per the investigator, may be considered for treatment continuation. Continuation of rucaparib treatment beyond progression will require separate patient consent. If the patient does continue to receive rucaparib, then the patient will continue treatment with rucaparib as described starting in [Section 9.5.5](#) and a Treatment Discontinuation Visit will occur at the end of all rucaparib treatment. Patients who continue treatment with rucaparib after radiologic disease progression will have the option of tumor tissue biopsy collection at time of first disease progression on study (requires additional consent). Tumor tissue will be processed locally as formalin-fixed paraffin-embedded (FFPE) tissue. Refer to the Pathology Charter for detailed sample handling instructions.

The following procedures will be performed:

- PRO collected using the BPI-SF ([Appendix 6](#)), FACT-P ([Appendix 7](#)), EQ-5D-5L ([Appendix 8](#)), and analgesic drug score instruments ([Appendix 9](#); should be completed before other procedures)
- Physical examination
- Weight
- Vital signs
- 12-lead ECG

- Tumor assessment if it has been ≥ 8 weeks (≥ 12 weeks if previous scan was after 24 weeks on study) since the last assessment and the reason for treatment discontinuation was other than radiographically confirmed disease progression.
- Concomitant medications and procedures
- ECOG performance status ([Appendix 3](#))
- PSA measurement
- Hematology
- Serum chemistry (fasting is not required)
- Urinalysis
- Plasma sample for ctDNA
- AE (inclusive of SAE and AESI) monitoring
- Optional tumor tissue biopsy collection after the time of disease progression (radiologic or clinical) and prior to initiation of any subsequent anticancer therapy (requires additional consent). Tumor tissue will be processed locally as FFPE tissue. Refer to [Section 9.11](#) for more information and to the Pathology Charter for detailed sample handling instructions.

9.6.2 28-Day Follow-up Visit

The following procedures will be performed for all patients at 28 (± 3) days after the last dose of rucaparib.

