9.6.3 Long-term Follow-up

Patients who complete a 28-Day Follow-up Visit after the last dose of rucaparib will continue in long-term follow-up as described below.

- If applicable, tumor assessment (using the same methodology as was used at initial study screening [eg, CT scan]) when the reason for treatment discontinuation was other than death or disease progression based on radiologic assessment and it has been ≥ 8 weeks (≥ 12 weeks if previous scan was after 24 weeks on study) since last scan or disease progression was noted on the last scan. Tumor assessment should continue to be performed at the end of every 8 calendar weeks (± 7 days) relative to Study Day 1 (Week 1) up to 24 weeks, then every 12 calendar weeks (± 7 days), until confirmed radiologic disease progression by modified RECIST Version 1.1 and/or PCWG3 (for bone lesions only) criteria, as assessed by the investigator, loss to follow-up, withdrawal, or study closure.
 - PRO assessments will also continue and coincide on days when tumor assessments are performed until confirmed radiographic disease progression. PRO using the BPI-SF ([Appendix 6](#)), FACT-P ([Appendix 7](#)), EQ-5D-5L ([Appendix 8](#)), and analgesic drug score instruments ([Appendix 9](#))
- All patients discontinued from treatment, regardless of reason, will be followed and information collected for subsequent treatments and survival every 12 weeks from last dose of rucaparib until death, loss to follow-up, withdrawal of consent from study, or closure of the study. Follow-up can be performed via the telephone and can be completed to coincide with scheduled tumor assessments and/or PRO during this period.
- SAEs related to study drug and AESIs are to be reported as specified in [Section 10.7](#).

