10.2.2 Radiographic PFS

rPFS is defined as the time from first dose of rucaparib to the date of first objective evidence of radiographic progression (soft tissue or bone lesion) or death due to any cause, whichever occurs first, plus 1 day. Radiographic disease progression includes confirmed bone disease progression and soft tissue disease progression adjudicated by IRR using the PCWG3 guidelines for bone disease and modified RECIST Version 1.1 for soft tissue disease. Patients without a documented event of progression will be censored on the date of their last adequate tumor assessment (i.e., radiographic assessment) or date of first dose of study drug if no post-baseline tumor assessments have been performed.

Patients who withdraw from treatment prior to radiographic progression will be followed for disease status and survival whenever possible. Only tumor scans (and deaths, for PFS analyses) prior to start of any subsequent anticancer treatment will be included. If a patient discontinues study drug due to a reason other than radiographic PD and subsequently begins another anticancer therapy (ACT) prior to a PFS event, that patient will be censored at the last scan prior to the start of ACT. However, scans/PFS events occurring more than 24 weeks after DC/stop of study drug and more than 24 weeks after their last previous scan but prior to start of subsequent ACT will not be included in the analysis and such patients will be censored at their last scan prior to the end of the 24-week window.

rPFS will be presented by gene mutation for all patients (separately, using IRR and Investigator assessments) and may also be presented by measurable disease status at Baseline.

A sensitivity analysis will be performed in which patients who have discontinued without radiographic progression, but who have had PSA progression, will be treated as having an event at the time of PSA progression.

rPFS will be summarized using Kaplan-Meier methodology and in the case of a low censoring rate it may be summarized with descriptive statistics.

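### Imaging stops on the investigator's call of progression, so IRR-read rPFS and DOR may run long where the two readers differ, and the protocol contradicts itself on scans for patients treated beyond progression

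*Protocol*

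**What the plan says.** **When scanning ends.** Protocol 9.1, Table 5 note l: "Radiologic assessments should continue for all patients until confirmation of radiographic progression per investigator assessment". Protocol 9.6.3 applies the same rule in long-term follow-up, "until confirmed radiologic disease progression by modified RECIST Version 1.1 and/or PCWG3 (for bone lesions only) criteria, as assessed by the investigator", and 9.9 repeats it. No section asks for IRR agreement before imaging stops.

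**Who reads the endpoints.** SAP 10.2.2: "Radiographic disease progression includes confirmed bone disease progression and soft tissue disease progression adjudicated by IRR". A patient without documented progression is censored at the last adequate tumor assessment. Deaths count as rPFS events if they precede new anticancer therapy, and scans after new therapy are excluded. SAP 10.2.1 censors DOR at the last assessment and names progression as its only event. Both endpoints are also to be presented by investigator assessment. The one rPFS sensitivity analysis adds PSA progression.

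**Bone.** Protocol Appendix 2 requires a later scan before an investigator's bone progression is confirmed: Week 17 for a Week 9 call, Week 25 for a Week 17 call, and 6 weeks on for later calls.

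**Treatment beyond progression.** Protocol 5.1.3 says: "These patients will continue to undergo all protocol required assessments specified in" Table 5, which includes scans. Protocol 9.6.1 says that "then the patient will continue treatment with rucaparib as described starting in" Section 9.5.5, which lists "Tumor assessment scans at the end of every 8 calendar weeks" and 12-weekly scans later. Protocol 7.4.4 keeps the protocol assessments "with the exception of radiographic assessments which may be performed per local standard of care".

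**The concern.** If the investigator calls soft-tissue progression and IRR does not see it on the same scan, the protocol requires no further imaging. The IRR analysis then censors the patient at the moment his physician judged him to be progressing. Both readers look at the same images, so an investigator's call plausibly signals that IRR would agree soon. Kaplan-Meier estimation assumes that a censored patient has the same outlook as those still followed, which would not hold here. IRR rPFS and IRR DOR describe how durable the IRR-read primary response is, and this single-arm trial has no comparator in which a shared bias could cancel.

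The conflict over imaging beyond progression adds to this. Two sites could follow the same kind of patient differently and both comply, so the amount of later imaging available to IRR would depend on which section a site reads.

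**Working it through.** The plan states no event count, power or discordance rate for rPFS or DOR, so there is no planned figure to reproduce. The model below shows direction and rough scale only.

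**Inputs**
- Scan weeks 8, 16, 24, 36, 48 (Protocol 5.1.3 and 9.5.5).
- Median time to IRR progression 9.8 months, exponential. This is the median rPFS for biomarker-positive patients in the study of another PARP inhibitor cited in Protocol 3.5, used only for scale. 9.8 × 52/12 = 42.47 weeks, so λ = ln 2 / 42.47 = 0.01632 per week.
- Death without progression, median 27.6 months (119.6 weeks): an assumption.
- A share d of patients is called by the investigator one scan before IRR would call them. The documents do not give d; I take 10% to 30%.

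**Progression-only endpoint (stand-in for DOR, measured here from first dose).** Let S_j = exp(−λ × week_j), giving 0.8776, 0.7702, 0.6759, 0.5557, 0.4568. With scans continued to IRR progression, the 12-month value is S_5 = 0.457.

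As planned, the risk set at scan j ≥ 2 is (1−d)S_(j−1) + d·S_j, because discordant patients due to progress at scan j were censored one scan before. The events are (1−d)(S_(j−1) − S_j). The Kaplan-Meier factor is therefore S_j / [(1−d)S_(j−1) + d·S_j]. The first scan contributes S_1, since no earlier on-treatment scan exists.

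For d = 0.3, the factors at weeks 16 and 24 are 0.7702 / (0.7 × 0.8776 + 0.3 × 0.7702) = 0.9110 each. At weeks 36 and 48 they are 0.8685 each. The product is 0.8776 × 0.9110² × 0.8685² = 0.549.

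**rPFS.** If all discordant patients switch therapy at once, multiply by survival free of death at 52 weeks, exp(−ln 2 × 52/119.6) = 0.740.

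| d | Progression-only: followed to IRR PD | As planned | Gap (points) | rPFS: followed to IRR PD | As planned | Gap (points) |
|---|---|---|---|---|---|---|
| 10% | 0.457 | 0.485 | 2.8 | 0.338 | 0.359 | 2.1 |
| 20% | 0.457 | 0.516 | 5.9 | 0.338 | 0.382 | 4.4 |
| 30% | 0.457 | 0.549 | 9.3 | 0.338 | 0.406 | 6.8 |

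Simulation of the same model (200,000 patients per scenario) gave 0.484, 0.516 and 0.550 for the progression-only endpoint, and 0.358, 0.382 and 0.407 for rPFS.

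**Variations (simulated, 10/20/30%)**
- Half of the discordant patients do not switch, and their deaths within 24 weeks count (median 6 months to death after the call, assumed): rPFS 0.356, 0.374, 0.391 against 0.34.
- Two-scan lead, all switching: rPFS 0.352, 0.366, 0.384 against 0.34; progression-only 0.477, 0.495, 0.518 against 0.46.
- Investigator calls unrelated to later IRR progression: no upward shift. The progression-only value stays at 0.46. rPFS stays at 0.34, or falls to 0.336, 0.327, 0.322 when half do not switch.

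**The case against.** The other side has several sound points.

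- The SAP already plans investigator-read rPFS and DOR, in which the investigator's progression is an event on the investigator's date. A reader might infer that nothing planned addresses disagreement between readers; that is not so. What remains is that these analyses change the reader for every patient, and for DOR also the set of responders. They allow a comparison but do not correct the IRR estimate or show how much of a difference comes from discordant censoring.
- A reader might infer that no protocol scan ever follows an investigator's call. For bone this is wrong, since confirmation needs a later scan. The exposure is mainly in soft tissue.
- Deaths before new therapy remain rPFS events, which limits that bias. DOR lists no such event.
- Scans after new therapy are excluded anyway, so longer imaging recovers events only in patients who have not switched.
- Protocol 5.1.3 already collects copies of all scans for IRR. It does not say that scans done under local practice after progression enter the IRR endpoints.
- The pooled ovarian results in Protocol 3.4.2.2 (57 of 106 responses by investigator, 44 of 106 by independent review) might be taken as a guide to discordance. They concern response in another cancer and say nothing about progression calls here.
- Both endpoints are secondary and descriptive. The IRR response rate and the two-stage rules do not depend on them.

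None of this removes the contradiction over imaging beyond progression.

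**Conclusion.** The documents establish two things: imaging ends on one reader's call while durability is also estimated from another's, and Protocol 5.1.3 (with 9.6.1 and 9.5.5) conflicts with 7.4.4. Upward bias in IRR rPFS and DOR is likely but is an inference. It requires that an investigator's call predicts IRR progression, and it vanishes if the call does not.

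A reader might go further and say that these curves do run long, by a known amount. The documents do not support that, because they give no discordance rate. The figures of about 2 to 7 points for rPFS and 3 to 9 points for a progression-only endpoint at 12 months rest on assumed discordance of 10% to 30%, a one-scan lead, exponential times and a borrowed median. A two-scan lead gives smaller gaps, roughly 1 to 5 and 2 to 6 points. The point is a cheap improvement to secondary estimates and leaves the primary analysis untouched.

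**What to change.** 1. **Protocol 5.1.3, 9.6.1 and 7.4.4.** Reconcile these so that all sites follow one imaging rule for patients treated beyond progression; which rule is for the sponsor to decide. In Table 5 note l, state that scans obtained after investigator progression and before new anticancer therapy, including those done under local care, go to IRR and are used for the IRR endpoints.
2. **SAP 10.2.1 and 10.2.2.** Add a prespecified sensitivity analysis of IRR rPFS and IRR DOR. Investigator radiographic progression that IRR does not share, with no later IRR-read scan, counts as an event on the investigator's date. This needs no extra imaging, so it also covers patients who switch therapy at once.
3. **SAP.** Tabulate progression by reader: both, investigator only, IRR only. This supplies the discordance rate now missing and would show if the problem is negligible.

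The cost is protocol wording, transfer of scans already obtained, one sensitivity analysis and one table, with no change to sample size or the primary analysis. The downside for the sponsor is that a less favourable rPFS or DOR figure may stand beside the main one.
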